### **3 STUDY DESIGN**

This is a Phase 2 randomized, double-blind, placebo-controlled, multicenter study to evaluate the efficacy and safety of pacritinib in hospitalized patients with severe COVID-19 with or without cancer. Severe COVID-19 is defined as confirmed disease in patients who are hospitalized with hypoxia ( $\text{SpO}_2 \leq 93\%$  on room air), respiratory rate  $>30$ ,  $\text{PaO}_2/\text{FiO}_2 <300$ , but do not require IMV.

Patients will be randomized 1:1 to receive pacritinib (400 mg QD on Day 1, then 200 mg BID from Day 2 to Day 14) + SOC or placebo + SOC stratified by age (< 60 years versus  $\geq 60$  years) and the 7-point ordinal scale of clinical status scale (baseline 3 or 4 versus 5). The study duration will be 8 weeks.

Assigned treatment will continue for up to Day 14 or until the patient experiences intolerable adverse events (AEs), withdraws consent, or initiates another investigational therapy, or until the study is terminated. Assigned therapy may be given for an additional 7 days (for a total of 21 days) with the approval of the Medical Monitor if, in the opinion of the investigator, the patient's clinical signs and symptoms are improving and the potential benefit outweighs the potential risk. In the event of hospital discharge, patients will complete treatment with the assigned therapy as an outpatient.

The primary endpoint is the effect of treatment on the proportion of patients who require IMV and/or ECMO or die by Day 28.

The study will be monitored by an IDMC comprising a multidisciplinary group of at least three voting members in the fields of hematology, infectious disease, and biostatistics. Additional personnel may be added to the IDMC at the request of the IDMC membership. The membership, roles, and responsibilities of the IDMC will be fully defined by an IDMC charter.

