Safety will be monitored with physical examinations, clinical laboratory assessments, and electrocardiogram (ECG) monitoring for inpatients. Patients who are discharged from the hospital while still on study will be monitored weekly. Outpatient monitoring will include telephone/videoconference contact and may also include review of the patient's electronic medical record. Laboratory and ECG assessments will not be required for monitoring outpatients, including those completing their course of study drug. Specified pacritinib/placebo dosage modifications will be followed to address identified abnormalities. AE data will be collected from the time of randomization through 30 days following the last dose of pacritinib/placebo. Serious adverse events (SAEs) assessed as related to pacritinib/placebo or study procedure by the investigator or Sponsor shall be followed until the event resolves, stabilizes or the patient is lost to follow-up. SAEs assessed as unrelated to pacritinib/placebo or study procedures shall be followed for 30 days after the last dose of pacritinib/placebo, or until

the event resolves, returns to baseline, stabilizes, or the patient is lost to follow-up, whichever comes first.

At the request of an investigator, and with agreement of the Chief Medical Officer at CTI, the assigned treatment for an individual patient may be unblinded for the purposes of discussing the ongoing care of that patient.

The approximate study duration for each patient will be 8 weeks. The estimated duration of the entire study is approximately 1 year and is subject to increase as patient enrollment increases.

The schedules of study assessments for all patients are provided in [Table 1](#).

[figure not shown]

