### **6.4 Drug Accountability**

At the Day 15 or EOT assessment, any unused pacritinib/placebo capsules will be returned to the pharmacy. Compliance with pacritinib/placebo will be reported by the site as the number of missed doses.

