#### **6.5.4 Dosage Management Guidelines for QTcF Interval Prolongation**

An ECG will be performed at Screening (Baseline), Days 3, 8, 15 (or End of Treatment [EOT]), 22, 28, and on the day of hospital discharge (for patients who will be continuing pacritinib/placebo as outpatient), and as clinically indicated.

Treatment should be modified as shown in [Table 4](#), as recommended by FDA in case of QTcF interval prolongation. Dose modifications for any instance of QTcF prolongation (irrespective of relationship to study drug) are also described in this section. Dose levels referenced in the

following tables refer to the following available doses: 200 mg BID, 100 mg BID, and 100 mg QD.

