#### 7.1.4.5 *End of Treatment*

- 7-point ordinal scale of clinical status
- Physical examination
- Tmax
- HRmax
- SpO2 in ambient air (if possible) (lowest value documented during the calendar day)
- SpO2 with oxygen supplementation (if applicable) (lowest value documented during the calendar day)
- ECG
- Serum chemistry, including sodium, potassium, chloride, bicarbonate, blood urea nitrogen, creatinine, glucose, calcium, and magnesium
- Liver function panel, including AST, ALT, alkaline phosphatase, total bilirubin, and albumin
- CBC, including WBC count, hemoglobin, hematocrit, and platelet count
- WBC differential
- Coagulation tests, including INR, PTT, and fibrinogen
- CRP

- Ferritin
- D-dimer
- IL-6
- Troponin-I
- LDH
- BNP
- Procalcitonin
- Triglycerides
- CK
- Documentation of oxygen delivery method, which may include nasal cannula, non-rebreather, non-invasive positive pressure ventilation (eg, CPAP or BiPAP), or IMV. If multiple delivery methods were used, the method that provides the highest concentration of oxygen will be documented.
  - Highest oxygen delivery flow rate (if on non-invasive oxygen)
  - Highest %FiO2 (if on CPAP, BiPAP, or IMV)
  - Highest positive end-expiratory pressure (PEEP; if on positive pressure ventilation)
  - Lowest partial pressure of oxygen (PaO2):FiO2 ratio (if applicable); if arterial blood gas (ABG) has been assessed while the patient was on IMV, then the PaO2 should be documented along with the FiO2 set on the ventilator at the time of the ABG assessment
- Administer pacritinib/placebo (Days 2 through 14; Pacritinib/placebo may be given for an additional 7 days [through Day 21] with the approval of the Medical Monitor if, in the opinion of the investigator, the patient's clinical signs and symptoms are improving and the potential benefit outweighs the potential risk.)
- Documentation of pacritinib/placebo dosing (Days 2 through 14; Pacritinib/placebo may be given for an additional 7 days [through Day 21] with the approval of the Medical Monitor if, in the opinion of the investigator, the patient's clinical signs and symptoms are improving and the potential benefit outweighs the potential risk.)
- AEs
- Concomitant medications

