## **7.5 Safety Analyses**

Safety will be assessed through 30 days of follow-up after the last dose of study treatment and assessed by the cumulative incidence, severity and seriousness of TEAEs, drug discontinuations, laboratory values, and clinical assessments.

Summaries will be tabulated by treatment arm and in total for the Safety Population.

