### **7.5.2 Laboratory Assessments**

Clinical laboratory evaluations will be summarized using descriptive statistics for all laboratory parameters including absolute measurements and changes from baseline by scheduled time of evaluation. Changes from baseline by scheduled time of evaluation will include last visit on-study, maximum post-treatment value, and minimum post-treatment value. Both scheduled and unscheduled post-treatment visits will be considered for the summaries of the maximum and minimum post-treatment values. Results will be presented in SI units.

Laboratory results will be graded according to NCI-CTCAE version 4.03 as applicable. A shift table, presenting the frequency tabulation for baseline to each timepoint and the worst post-treatment value according to the NCI-CTCAE grade, will be provided for selected clinical laboratory tests. For select parameters (e.g. glucose), separate shift tables indicating hyper- and hypo-directionality of change may be produced. Both scheduled and unscheduled post-treatment visits will be considered in tabulation of the worst post-treatment value.

Clinical laboratory evaluations in SI units will be listed, including high and low flags, CTCAE grades where applicable, and the corresponding normal range.

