#### **7.5.4      *Electrocardiograms***

The frequency distribution of abnormal mean QTcF interval measurements on study (after the first study drug treatment through the last dose of study drug) will be summarized. That is, the proportion of subjects with the worst mean QTcF interval on study will be reported, and the following QTcF intervals will be tabulated by treatment arm:

- A measured value
  - > 450 ms
  - > 480 ms
  - > 500 ms
- Change
  - > 0 and  $\leq 10$  ms above baseline
  - > 10 and < 20 ms above baseline
  - $\geq 20$  ms above baseline

- > 30 ms above baseline
- > 60 ms above baseline

Plots of the QTcF across study day (Day8, Day 15, Day 22 and Day28 )will also be presented for each treatment arm.

ECG assessments including clinical significance will be listed by patient.

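### The worst-QTcF table stops at the last dose, so inpatients who finish treatment lose the ECG scheduled for the next day, taken near trough drug level

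*SAP*

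**What the plan says.** SAP 7.5.4 tabulates, by arm, the worst QTcF "on study (after the first study drug treatment through the last dose of study drug) will be summarized". The rows are absolute thresholds (>450, >480, >500 ms) and categories of change from baseline, including >30 and >60 ms. The same section also plots QTcF at Days 8, 15, 22 and 28 and lists all ECGs by patient.

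The protocol calendar is as follows:
- **Dosing** (Protocol 3): 400 mg on Day 1, "then 200 mg BID from Day 2 to Day 14". A 7-day extension to Day 21 is possible with Medical Monitor approval.
- **ECGs** (Protocol 6.5.4): "An ECG will be performed at Screening (Baseline), Days 3, 8, 15 (or End of Treatment [EOT]), 22, 28". Table 1 and section 7.1.4.4 also list Day 15 as an inpatient ECG day.
- **End of treatment** (Protocol 6.4): "At the Day 15 or EOT assessment, any unused pacritinib/placebo capsules will be returned to the pharmacy".
- **After discharge** (Protocol 3): "Laboratory and ECG assessments will not be required for monitoring outpatients, including those completing their course of study drug".

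Other safety windows in the SAP are wider. Section 7.5 says "Safety will be assessed through 30 days of follow-up after the last dose of study treatment". Section 7.5.2, on laboratory values, says "Both scheduled and unscheduled post-treatment visits will be considered in tabulation of the worst post-treatment value". Section 6.3.1 counts adverse events as treatment-emergent up to 30 days after the last dose. Section 7.5.3 takes worst vital signs from the first treatment day onward, with no cut at the last dose.

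**The concern.** The ECG that marks the end of treatment is scheduled for the day after the last planned dose. The table closes on the day of the last dose, so the two miss each other by one day. The lost value is the only routinely scheduled ECG reflecting the second week of a 14-day course, and it is taken while drug exposure is still close to what it was during dosing.

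An ECG that leads to a hold from which dosing never resumes is lost in the same way if it was taken before that day's dose. It then falls after the last dose and misses the >500 ms row.

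QTc prolongation is a named pacritinib risk in Protocol 6.5.2 and has its own dose-management table (Table 4). A reader of the study report would take the per-arm threshold counts as the summary of that risk. Removing observations from a worst-value table cannot raise a threshold count, so any error understates the number of patients above >450, >480, >500, >30 or >60 ms.

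**Working it through.** **Step 1. The calendar.** Scheduled inpatient post-baseline ECG days are {3, 8, 15, 22, 28}.

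| Last dose | Counted now | Counted with last dose + 3 days |
|---|---|---|
| Day 14 | 3, 8 (2 of 5) | 3, 8, 15 (3 of 5) |
| Day 21 (extended) | 3, 8, 15 (3 of 5) | 3, 8, 15, 22 (4 of 5) |

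The excluded ECG is 15 − 14 = 1 day, or 22 − 21 = 1 day, after the last dose.

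**Step 2. Who is affected.** Only patients still in hospital on Day 15 (or Day 22) have the ECG to lose. Patients discharged earlier have no required ECG. Patients whose end-of-treatment ECG is done on a dosing day may keep it, since the visit list in Protocol 7.1.4.5 includes "Administer pacritinib/placebo (Days 2 through 14". At most one scheduled ECG near trough is lost per patient.

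**Step 3. Drug level at the excluded ECG.** Protocol 1.2.3 gives a mean elimination half-life of about 34 h, from single doses in healthy subjects. ECG clock times are not given, so I assume a gap of 12 to 24 h after the last evening dose. With twice-daily dosing, 12 h after a dose is the ordinary pre-dose point, whatever the pharmacokinetic model.

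First-order decay, fraction left = 0.5^(t/34):
- 12 h: 0.5^(12/34) = 0.783
- 24 h: 0.5^(24/34) = 0.613

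Adding up the planned doses (one compartment, instant absorption; 400 mg at t = 0, then 200 mg every 12 h from t = 24 h to t = 324 h, the Day 14 evening dose) gives the amount in mg-equivalents:
- Day 8 pre-dose (t = 168 h): 696.3
- Day 8 just after the dose: 896.3
- Day 15 at 12 h (t = 336 h): 720.8
- Day 15 at 24 h (t = 348 h): 564.4

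Ratios of Day 15 to Day 8:
- to pre-dose: 720.8/696.3 = 1.035 and 564.4/696.3 = 0.811
- to just after the dose: 720.8/896.3 = 0.804 and 564.4/896.3 = 0.630

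Sensitivity to half-life:

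| Half-life (assumed) | Against Day 8 pre-dose, 12 h / 24 h | Against Day 8 just after dose, 12 h / 24 h |
|---|---|---|
| 20 h | 1.004 / 0.662 | 0.661 / 0.436 |
| 34 h | 1.035 / 0.811 | 0.804 / 0.630 |
| 50 h | 1.101 / 0.932 | 0.917 / 0.776 |

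The Day 15 ECG is therefore one more reading at exposure comparable with the counted Day 8 pre-dose level. It is not a reading at higher exposure: Protocol 3.1 says steady-state-equivalent levels are reached on Day 1.

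**Step 4. What a 3-day window admits and keeps out.**
- 72 h: 72/34 = 2.1 half-lives, 0.5^(72/34) = 0.230, so the lowest level admitted is about 23%.
- Day 22 after a Day 14 stop (192 h): 0.5^(192/34) = 0.020, kept out.
- Day 28 after a Day 21 stop (168 h): 0.5^(168/34) = 0.033, kept out.

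**The case against.** The strongest reply is that SAP 7.5.4 sets an on-treatment window in plain words, so this is a choice and not a contradiction. Section 7.5 is a general sentence that does not name ECGs. In section 7.5.2, post-treatment can be read as after the start of treatment. A 3-day window would not match either section, since it also limits the table to the time around treatment. All of this is fair. What remains is that no other worst-value table in the SAP stops at the last dose, and no reason is given for the ECG table doing so.

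A second reply is that little is lost. Both disputed visits appear in the plots, and every ECG is listed. A hold for QTcF of 501 msec or more fits the adverse-event definition in Protocol 8.1.1 and should reach the treatment-emergent event tables in SAP 7.5.1. This stands for values at or above 501 ms. But plots and listings give no threshold counts by arm, and values below 501 ms trigger no hold under Table 4, so event reporting need not capture them.

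A third reply is that the effect on the counts is not shown. The cut applies to both arms, and the drug-level figures rest on a one-compartment simplification (Protocol 1.2.1 describes two compartments) and assumed ECG times. At a 20 h half-life and a 24 h gap the level is only 44% of the Day 8 level just after dosing, so the description as near trough is weaker at that end. The model's pre-dose level also climbs from about 430 on Day 3 to 696 on Day 8, which fits poorly with the Day 1 steady-state statement. These limits stand. They bear on the size of the effect, not on the calendar or the direction of the understatement.

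Finally, last dose + 1 day would capture the same scheduled ECGs. That is correct for patients who take every dose. Three days also covers those whose final doses were missed or held.

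**Conclusion.** The concern holds. For inpatients who complete 14 or 21 days, the table excludes a scheduled ECG taken one day after the last dose. Its threshold counts can only be equal to or lower than they would be with that ECG included. The drug level at that ECG is about 81% to 104% of the Day 8 pre-dose level at a 34 h half-life, and 66% to 110% across assumed half-lives of 20 to 50 h. This assumes a 12 to 24 h gap, one compartment and instant absorption.

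The calendar finding does not depend on the drug-level model. The number of patients affected and any between-arm effect cannot be computed from the documents. The consequence is limited to one descriptive table with no hypothesis test, mainly to values below 501 ms at one visit. It should be fixed because the risk is a named one and the correction is cheap.

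**What to change.** In SAP 7.5.4, close the window 3 days after the last dose (about 2 half-lives) instead of at the last dose. State that it includes:
- the Day 15/EOT ECG after a Day 14 stop and the Day 22 ECG after a Day 21 stop;
- unscheduled ECGs within the window;
- any ECG that prompted a hold or stop of study drug.

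The strict on-dose table can stay as a supplement. If the sponsor prefers to keep the last-dose cut for the main table, the SAP should give the reason.

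The cost is one sentence and a date filter on data already collected. Reported rates of QTcF prolongation may rise slightly, and some ECGs with as little as about 23% of drug remaining will be admitted. Scheduled ECGs near washout stay out.

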### **7.5.5 Other Safety Assessments**

If applicable, other safety assessments will be listed by patient.

## **8 GENERAL INFORMATION**

### **8.1 Statistical Software**

The generation of analysis datasets and analysis tables, figures, and listings (TFLs) will be done using SAS® version 9.4 or higher. The Medpace standard operating procedures (Medpace Standard Operating Procedures GL-DS-02-S4 and GL-DS-03-S3) will be followed for the validation of all SAS programs and outputs.

### **8.2 Format of Tables, Listings, and Figures**

The format of tables, listings, and figures will be described in a stand-alone programming specifications document that will be prepared before database lock.

## **9 CHANGES FROM PROTOCOL-SPECIFIED ANALYSIS**

No changes from the protocol-specified analysis are planned.

## 11 APPENDIX 1: IMMUNOMODULATORY AGENTS

Immunomodulatory agent usage will be identified based on concomitant medications that are classified according to the following WHODD preferred names.

**Table 8 MedDRA Preferred Term List for Immunomodulatory Agents**

Immunomodulatory Agent Category	Preferred Names(s)*
Corticosteroids	Decadron, Dexamethason, Hydrocortisone, Metholprednisolne, Prednisone, Solumedrol
IL-6 inhibitors	Tocilizumab
IL-1 inhibitors	Anakinra
Antiretrovirals	Remdesivir

\*WHO-DDE B3, March, 2020.
